8.4 Withdrawal of individual subjects

Subjects can leave the study at any time for any reason if they wish to do so without any consequences. The investigator can decide to withdraw a subject from the study for urgent medical reasons.

8.5 Replacement of individual subjects after withdrawal

Subjects will not be replaced.

8.6 Follow-up of subjects withdrawn from treatment

Not applicable.

8.7 Premature termination of the study

The study will be prematurely terminated in case of problems regarding the inclusion or participation of patients.. Also, the study will be terminated if it is temporarily suspended for reasons of subjects' safety and the accredited METC gives a negative decision after assessing the reasons that led to the temporary suspension.

9. SAFETY REPORTING

9.1 Temporary halt for reasons of subject safety

In accordance to section 10, subsection 4, of the WMO, the sponsor will suspend the study if there is sufficient ground that continuation of the study will jeopardise subject health or safety. The sponsor will notify the accredited METC without undue delay of a temporary halt including the reason for such an action. The study will be suspended pending a further positive decision by the accredited METC. The investigator will take care that all subjects are kept informed.

9.2 AEs, SAEs and SUSARs

9.2.1 Adverse events (AEs)

Adverse events are defined as any undesirable experience occurring to a subject during the study, whether or not considered related to study procedure. All adverse events reported spontaneously by the subject or observed by the investigator or his staff will be recorded.

9.2.2 Serious adverse events (SAEs)

A serious adverse event is any untoward medical occurrence or effect that

- results in death;
- is life threatening (at the time of the event);
- requires hospitalisation or prolongation of existing inpatients' hospitalisation;
- results in persistent or significant disability or incapacity;
- is a congenital anomaly or birth defect; or
- any other important medical event that did not result in any of the outcomes listed above due to medical or surgical intervention but could have been based upon appropriate judgement by the investigator.

An elective hospital admission will not be considered as a serious adverse event.

Only study related (S)AE's will be reported immediately. This means all (S)AE's related to participation in this study protocol, meaning from the venepuncture, will be reported. All other (S)AE's will not be reported, since the study procedure is considered to be of very low risk.

The sponsor will report these SAEs through the web portal *ToetsingOnline* to the accredited METC that approved the protocol, within 7 days of first knowledge for SAEs that result in death or are life threatening followed by a period of maximum of 8 days to complete the initial preliminary report. All other SAEs will be reported within a period of maximum 15 days after the sponsor has first knowledge of the serious adverse events.

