4.4 Sample size calculation

A formal sample size calculation cannot be done, since it is currently unknown what the variation in immunological response is children with COVID-19 or MIS-C and how this relates to outcome measures. Based on the number of participating sites and the inclusion rate in the first wave of the epidemic, we expect to be able to include at least 60 children in total, and 30 children for the immunological part of the study.

We expect the rate of consent for blood withdrawal to be higher in patients with more severe disease (since the blood can be taken during routine blood withdrawal and no separate venapuncture will be needed). Therefore, based on inclusion rates for the related COPP-study, we estimate we will be able to include at least 10 patients with MIS-C, 10 patients with moderate to severe COVID-19 and 10 patients with mild COVID-19. Clinical information will be available for all of the patients included in the immunological part of the study.

If we will have reached 60 inclusions for the immunological part of the study within the first 18 months of the study, we will do an interim analysis to determine if more inclusions are needed. Since this is an exploratory study, no formal maximal number of inclusions can be given, but based on previous inclusions in de COPP-study and the expected course of the epidemic we do not expect to reach a higher inclusion than 60 in this timeframe.

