8.3 Study procedures

1. **Patients will be included** in the study in case of SARS-CoV-2 positive test, or fulfilling a clinical diagnosis of COVID-19, or fulfilling a diagnosis of MIS-C; and after obtaining informed consent (IC) from both guardians and/or patient. Because only one parent can accompany the hospitalized child (due to COVID-19 restrictions), initially it is only one guardian who will sign the consent form. If applicable, the signature of the second guardian will be collected as soon as possible. Consent can be given for just the clinical part of the study (with or without consent for follow-up studies); or for both the clinical and immunological part of the study.
2. **Clinical data** from the subject at time of presentation in the hospital will be noted in a case report form. In case of a diagnosis of COVID-19 after hospital presentation the data will be collected from the electronic medical record. Summarized this data will contain:
 - a. Patient characteristics and risk factors: age, gender, height, weight, exposure to known COVID-19 cases, prior medical history, medication.
 - b. Clinical features at presentation: symptoms, vital signs, physical examination, imaging results, laboratory results.
 - c. Course of illness: clinical symptoms, vital signs, physical examination, imaging results, laboratory result, the need for respiratory support, the need for IC treatment, medication, aerosol treatment, co-morbidity and outcome.Clinical data will be recorded in Castor. For details regarding the datamanagement plan see **Appendix A**.

When patients are being admitted to the IC, additional information about the neurological tests that have been performed (standard care) will be collected for

this study. Guardians and/or children can give consent for this data collection in our standard consent form.

3. **Blood samples** for this study will be collected after confirmation of the diagnosis COVID-19 or MIS-C and after the patient and/or the caregiver have consented for participation in this study. If possible, the collection of the blood sample will be combined with a blood sample collection for routine clinical care and/or will be drawn from an indwelling venous catheter. In this case, there will be no additional burden to the patient.

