If after confirmation of the diagnosis and obtainment of informed consent, no blood sample collection is scheduled for routine clinical care and there is no venous catheter present from which the blood can be drawn, a venepuncture will be done to collect material for this study. In this case, there will be some burden to the patient. To ensure that this burden is minimal, we will apply a topical anaesthetic (lidocaine/prilocaine or lidocaine/tetracaine as per local guidelines) prior to the procedure. Also, we will instruct local researchers to engage in “positive language” before and during the procedure (See **Appendix B**).

The amount of blood drawn depends on the body weight of the patient. With these amounts, we remain well below the recommended maximum of 3% of total blood volume in all weight categories (8). If the local investigator does not succeed in obtaining the required amount of blood, a smaller sample will be collected. In that case, immunological investigations will need to be prioritized (see 8.1.1 for details regarding priorities).

body weight	EDTA (mL)	serum (mL)	total volume (mL)
3-5 kg	4	1	5
5-10 kg	5	2	7
10-20 kg	10	5	15
20-40 kg	20	10	30
>= 40 kg	30	10	40

Scarce material from blood samples will be stored in local centers. They will be used to retrospectively analyze additional laboratory parameters associated with severity of disease and outcome, such as cytokine levels (particularly IL-6) and medication concentrations (particularly chloroquine).

4. **Timing of sampling**

We aim to collect the sample *as soon as possible* after inclusion in the study, preferably before any *immune modulatory medication* has been administered. This will enable us to determine the immunological profile in the *acute phase* of the illness. The acute phase of the illness is defined as: at presentation of the patient (in case of screening, asymptomatic patient or ambulatory patient) OR ongoing symptoms (in case of acute COVID-19) OR ongoing signs of hyperinflammation (in case of MIS-C). The local investigator will note the exact date and time of blood sampling in the case report form.

For a Standard Operating Procedure regarding the blood draw and logistics, see **Appendix C**.

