9.4 Follow-up of adverse events

All AEs will be followed until they have abated, or until a stable situation has been reached. Depending on the event, follow up may require additional tests or medical procedures as indicated, and/or referral to the general physician or a medical specialist. SAEs need to be reported till end of study within the Netherlands, as defined in the protocol

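### The expedited SAE reporting rule is worded around a venepuncture, although the preferred sampling routes are an indwelling catheter or a combined routine draw; the sections on which SAEs are reported also disagree

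*Protocol*

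**What the plan says.** **The reporting rule.** Protocol 9.2.2 limits immediate reporting to study-related events and then explains the term: "This means all (S)AE's related to participation in this study protocol, meaning from the venepuncture, will be reported". The next sentence closes the list: "All other (S)AE's will not be reported, since the study procedure is considered to be of very low risk". The time limits that follow apply to this set: 7 days for fatal or life-threatening SAEs (plus up to 8 days to complete the report) and 15 days for the rest.

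**How the blood is taken.** Protocol 8.3, item 3, puts the combined draw first: "If possible, the collection of the blood sample will be combined with a blood sample collection for routine clinical care". As an addition or alternative, the sample "will be drawn from an indwelling venous catheter. In this case, there will be no additional burden to the patient". Only when no routine draw is scheduled and no catheter is in place does the fallback apply: "a venepuncture will be done to collect material for this study. In this case, there will be some burden to the patient". Section 4.4 expects more consent to sampling in sicker children, "since the blood can be taken during routine blood withdrawal and no separate venapuncture will be needed".

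**Other sections on SAEs.**
- Section 9.2.1 has all adverse events that are volunteered or observed recorded, related or not.
- Section 9.4 says "SAEs need to be reported till end of study within the Netherlands, as defined in the protocol".
- Section 12.4 lists serious adverse events in the yearly progress report to the ethics committee, with no limit by cause.
- Section 9.3 marks the annual safety report as not applicable.

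**The concern.** The rule starts from a sound idea, events related to participation, and then narrows it to one technique. That technique is the one the protocol hopes to avoid. A local investigator who follows 9.2.2 to the letter could decide that a serious event caused by drawing study blood through a catheter is not reportable, because there was no venepuncture.

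What is at stake is how quickly such an event reaches the sponsor and the ethics committee. Section 9.1 obliges the sponsor to suspend the study if there is sufficient ground to think that subjects are in danger, and the sponsor can act only on what it is told. Sections 11.4 and 11.5 describe the risk as negligible and ask for dispensation from subject insurance, so the reporting rule should cover every way in which the study takes blood. No objective, endpoint or analysis is affected.

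**Working it through.** The point is one of wording, and the protocol gives no figure to reproduce. The check sets each sampling route against the rule, then compares the SAE sections with one another, then looks at the size of the exposure.

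**Step 1. Routes (8.3, item 3) against the rule (9.2.2)**

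| Route | Place in 8.3 | Covered by the literal rule? |
|---|---|---|
| Drawn from an indwelling catheter | Preferred | No: nothing is punctured for the study |
| Study volume added to a routine draw | Preferred | Unclear: the routine draw may itself be a venepuncture, but not one done for the study |
| Separate study venepuncture | Fallback | Yes |

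The topical anaesthetic is described, in the Summary and in 8.3, only for the separate venepuncture: "we will apply a topical anaesthetic (lidocaine/prilocaine or lidocaine/tetracaine as per local guidelines) prior to the procedure". It therefore belongs to the route that the rule covers.

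**Step 2. The SAE sections against one another**

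- 9.2.2: events other than those from the venepuncture are not reported. No time frame or recipient qualifies this.
- 9.4: SAEs are reported until the end of the study. The closing words may refer to the definition of the end of the study or to the set of reportable SAEs; the grammar allows both. On the first reading 9.4 conflicts with 9.2.2. On the second it inherits the narrow rule.
- 12.4: SAEs go into the yearly report, with no restriction. Taken at face value, this conflicts with 9.2.2.
- 9.2.1: events are recorded. This keeps them in the study record but sets no time limit for reporting.

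**Step 3. Size of the exposure**

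Inputs: the volumes in the 8.3 table and the lowest weight in each band. The protocol gives no blood volume per kg, so 65 to 90 mL/kg is an assumption.

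Share of blood volume = study volume / (weight × blood volume per kg).

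| Lowest weight | Study volume | mL/kg | Share at 90 mL/kg | Share at 65 mL/kg |
|---|---|---|---|---|
| 3 kg | 5 mL | 1.67 | 1.85% | 2.56% |
| 5 kg | 7 mL | 1.40 | 1.56% | 2.15% |
| 10 kg | 15 mL | 1.50 | 1.67% | 2.31% |
| 20 kg | 30 mL | 1.50 | 1.67% | 2.31% |
| 40 kg | 40 mL | 1.00 | 1.11% | 1.54% |

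Example: 5 / (3 × 65) = 5 / 195 = 2.56%. The 3 kg case would pass 3% only if blood volume were below 5 / (3 × 0.03) = 55.6 mL/kg. The protocol's statement that study draws stay below 3% holds over the assumed range. Blood taken for routine care at the same time is not counted here.

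The Summary gives an upper volume of 50 mL where the table stops at 40 mL. The two must be reconciled, but the difference does not change this point: 50 mL at 40 kg is 1.39% to 1.92%.

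**The case against.** The best defence is that the gloss is shorthand. Blood sampling is the only invasive study procedure, and the governing words are about events related to participation, so a sensible investigator would report a catheter complication caused by the study draw. The sentence excluding other events follows one about immediate reporting and may mean only that they are not reported immediately; on that reading 12.4 is not contradicted. Adverse events are recorded under 9.2.1 and followed up under 9.4, so little would be lost. The sample is single and small.

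Much of this stands, and it limits the point to expedited reporting. It does not remove the defect. The gloss names one technique, the exclusion carries no qualifier, and 4.4 and 8.3 themselves distinguish a separate puncture from the other routes.

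A reader might infer four stronger things that the documents do not support:

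- **That harm from the topical anaesthetic is also excluded.** It is tied to the separate venepuncture, and an event from it can reasonably be read as part of that procedure.
- **That study-caused harm goes entirely unreported.** Sections 9.2.1 and 12.4 provide for recording and for yearly reporting of SAEs.
- **That two thirds of sampled children fall outside the rule**, by counting the 20 children with MIS-C or moderate to severe COVID-19 among the 30 in 4.4. That section predicts higher consent in sicker children. It gives no share by route, and a routine draw may be a venepuncture.
- **That the study would conclude negligible risk because its rule hid the events.** No safety endpoint or safety conclusion is planned. The statement on risk is made in advance, for the ethics review.

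**Conclusion.** The point holds as a drafting fault in a stated safety rule. A study-related SAE from a catheter draw is outside the 7-day and 15-day reporting as written, and one from added volume at a routine draw is ambiguous. The flat statement in 9.2.2 that other events are not reported also fits badly with 9.4 and 12.4.

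Confidence in the wording fault is high, since it rests on the text of 9.2.2 and 8.3 alone. Its importance is minor. The absolute risk is low, and the volume figures, which depend on the assumed 65 to 90 mL/kg, agree with the protocol's own 3% limit and are not evidence of likely harm. How many children would be sampled by each route cannot be derived from the protocol, so no share of the cohort is given.

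**What to change.** 1. In 9.2.2, replace the gloss that ties relatedness to the venepuncture with: *meaning from the withdrawal of study blood by any route (separate venepuncture, indwelling catheter, or volume added to a routine draw), including preparation for it*.
2. Reconcile 9.2.2, 9.4 and 12.4 on which SAEs are reported, to whom and when. In particular, say whether the exclusion in 9.2.2 concerns only expedited reporting, which SAEs 9.4 means, and which SAEs enter the annual progress report.

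This takes a few sentences in an amendment and a matching line in the site instructions. The downside is a few more events to assess for relatedness. Nothing in the sampling, the endpoints or the analysis has to change.

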9.3 Annual safety report

Not applicable

9.4 Follow-up of adverse events

All AEs will be followed until they have abated, or until a stable situation has been reached. Depending on the event, follow up may require additional tests or medical procedures as indicated, and/or referral to the general physician or a medical specialist. SAEs need to be reported till end of study within the Netherlands, as defined in the protocol

10. STATISTICAL ANALYSIS

10.1 Primary study parameter(s)

Statistical analysis of the primary objective: immunological profiling of children with COVID-19 or MIS-C:

1. Relative distributions of immune cell subsets will be obtained by multicolor flow cytometry. Data will be imported in R for statistical analysis. Cytosplore will be used for clustering and dimensionality reduction (9). Distributions will be compared to available reference values (normal distribution of immune cell subsets in children, adjusted for age) and will be compared across subgroups (mild COVID-19, moderate to severe COVID-19 and MIS-C).
2. Cytokine levels will be analyzed in R and SPSS. Levels will likely be non-normally distributed, in which case non-parametric Kruskal-Wallis tests will be done for comparison across groups. To adjust for multiple testing, we will use the two-stage step-up method of Benjamini *et al* (10). Cytokine levels will be compared to normal values as already available for healthy adults, and across the subgroups(mild COVID-19, moderate to severe COVID-19 and MIS-C).
3. Levels of neutralizing antibodies will be compared across subgroups (mild COVID-19, moderate to severe COVID-19 and MIS-C) using ANOVA in SPSS.

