4. STUDY POPULATION

4.1 Population (base)

Currently, 53 hospitals are participating in the COPP-study. From April through December 2020, there have been 157 inclusions (with some children included twice if they were transferred between hospitals). Of the 48 COPP-sites, 13 have currently expressed interest in participating in the COPP-IMM study, including five academic centers. The exact number of children that will be included in COPP-IMM depends on the course of the epidemic, but based on this data, we expect to be able to include about 60 children for the observational part of the study. We expect to be able to obtain informed consent for blood withdrawal in ~50% of these patients, so 30 patients.

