8.1.1 Main study parameter/endpoint

For the clinical observational part of the study (analyzed together with data from the COPP-study) the main study parameters are:

- To describe the clinical features of the COVID-19 in hospitalized and outpatient pediatric patients in the Netherlands.
- To describe the clinical course of the COVID-19 in hospitalized and outpatient pediatric patients.
- To describe the response to treatment, including supportive care.
- To determine risk factors for severe disease in children with COVID-19.

For the immunological part of the COPP-IMM study, we will obtain a detailed immunological profile of children presenting to Dutch hospitals with acute SARS-CoV-2 infection or with a SARS-CoV-2 related post-infectious inflammatory syndrome. Since clinically relevant pediatric COVID-19 is rare and we will have a limited amount of material available from each patient, we will do this in a two-tiered approach. This will enable us to choose which will be the most informative in-depth immunological analysis following a more general screening of the innate and adaptive immune system.

In the FIRST TIER we will do a general assessment of the immune system. In this general assessment we will do the following investigations:

1. Detailed phenotypical analysis of the cells of the innate and adaptive immune system using multicolor flow cytometry. We will use the EuroFlow protocol PID Orientation

tube to be able to identify and quantify the main leukocyte and lymphocyte subsets, using 12 markers: CD27, CD45RA, CD8, IgD, CD16, CD56, CD4, IgM, CD19, CD3, CD45, and TCR $\gamma\delta$. This will enable us to identify B-cells (including B-cell subsets), T-cells (including T-cell subsets), NK-cells, monocytes (including non-classical CD16+ monocytes), dendritic cells, basophils, neutrophils and eosinophils (minimum of 4 mL of EDTA needed).

2. Multiplex analysis of inflammatory cytokines in serum using Luminex bead arrays (in excess of 100 analytes, to determine Th1/Th2 and innate responses) (200-400 uL).
3. Quantitative and qualitative (affinity) analysis of anti-SARS-CoV-2 antibodies in serum and potential cross-reactive antibodies to other coronaviruses (200-400 uL).

Depending on the results of the investigations in the first tier, we will choose one of the following in-depth immunological analyses for the SECOND TIER:

[figure not shown]

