10.2 Secondary study parameter(s)

Secondary objectives:

- (1) To correlate the immunological profiles with detailed clinical parameters
Adjusted relative risks for specific outcome measures (such as the need for supplemental oxygen, ICU admission, duration of hospital stay) in association with immunological profiles will be calculated using logistic regression.
- (2) To determine if there are immunological targets of therapy for children with severe COVID-19 or MIS-C: Evaluate the levels of certain drug-targetable cytokines using Kruskal-Wallis tests in SPSS (eg IFN-gamma, IL-1beta, TNF-alpha) and perform agglomerative hierarchical clustering using average linking (Between Groups) with squared Euclidean distance to determine subgroups of patients with specific inflammatory profiles..
- (3) To determine if hyperinflammation in MIS-C is different from the inflammatory response in severe pediatric COVID-19: non-parametric Kruskal-Wallis tests will be done for comparison across groups (in R and SPSS).

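### At about 10 children per group, default chi-square Kruskal-Wallis p-values would make the cytokine false-discovery step over-conservative when few cytokines differ or effects are moderate; permutation p-values avoid this (minor)

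*Protocol*

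**What the plan says.** Section 10.1 item 2 of the Protocol covers cytokine levels, part of the primary immunological profile. It expects non-normal data, and in that case "non-parametric Kruskal-Wallis tests will be done for comparison across groups. To adjust for multiple testing, we will use the two-stage step-up method" of a cited paper. The analysis is to be run in R and SPSS across three subgroups: mild COVID-19, moderate to severe COVID-19, and MIS-C. The false-discovery level is not given. Nor does the section say whether the p-values are asymptotic, exact or Monte Carlo.

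Section 8.1.1 describes the panel as "in excess of 100 analytes". Section 4.4 expects "at least 10 patients with MIS-C, 10 patients with moderate to severe COVID-19 and 10 patients with mild COVID-19". It calls the study exploratory, gives no formal sample size calculation, and says of the first 18 months that "we do not expect to reach a higher inclusion than 60 in this timeframe".

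**The concern.** The Kruskal-Wallis statistic is usually referred to a chi-square distribution with 2 degrees of freedom when there are three groups. At 10 per group that is close to correct at the 5% level, so the choice looks harmless. A step-up procedure over 100 tests works much further out: the first discovery needs a p-value of about 0.0005. There the small-sample distribution of the statistic has a thinner tail than chi-square, so the approximate p-value is too large.

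At stake is sensitivity in a primary analysis of scarce paediatric samples. The samples could contain cytokine differences that a more accurate p-value, on the same test and the same data, would have declared.

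**Working it through.** **The plan's own figure.** Section 4.1 expects about 60 children and says "We expect to be able to obtain informed consent for blood withdrawal in ~50% of these patients, so 30 patients". So 60 × 0.5 = 30 = 10 + 10 + 10, which agrees with section 4.4.

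**Inputs from the Protocol.** Three groups of 10 (4.4); m = 100 tests as a lower bound for the panel (8.1.1); Kruskal-Wallis and the two-stage step-up procedure (10.1).

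**Assumptions not in the Protocol.** False-discovery level q = 0.05 (0.10 as a check); a shift in one group only; the number of truly different analytes; no ties; chi-square as the software default.

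**Step 1: the two p-values.** With rank sums Rᵢ, group sizes nᵢ and N = 30, H = 12/(N(N+1)) · Σ Rᵢ²/nᵢ − 3(N+1). The chi-square p-value on 2 df is exp(−H/2). The exact p-value comes from full enumeration of the 30!/(10!)³ = 5,550,996,791,340 arrangements. Chi-square p divided by exact p is:

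| exact p | 0.05 | 0.01 | 0.005 | 0.001 | 0.0005 | 0.0001 |
|---|---|---|---|---|---|---|
| ratio | 1.07 | 1.34 | 1.53 | 2.3 | 2.9 | 5.3 |

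**Step 2: where the procedure operates.** With q′ = q/(1+q) = 0.05/1.05 = 0.0476, and k discoveries in both stages, the cut-off is k·q′/(100 − k). For k = 1 this is 0.0476/99 = 0.00048.

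| discoveries k | cut-off | ratio when exact p meets it | ratio when chi-square p meets it |
|---|---|---|---|
| 1 | 0.00048 | 2.9 | 5.6 |
| 5 | 0.0025 | 1.8 | 2.3 |
| 10 | 0.0053 | 1.5 | 1.7 |
| 30 | 0.020 | 1.2 | 1.2 |
| 50 | 0.048 | 1.1 | 1.1 |

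In the first row, an exact p of 0.00048 corresponds to a chi-square p of 0.0014 (0.0014/0.00048 = 2.9). A chi-square p of 0.00048 corresponds to an exact p of 0.000086 (0.00048/0.000086 = 5.6). With q = 0.10 and k = 1 the two ratios are 2.4 and 3.7. With 6/12/12 children the ratio at 0.0005 is 3.2. With 20 per group it is 1.5 at 0.001 and 1.7 at 0.0005.

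**Step 3: effect on sensitivity.** Simulation used 1,500 studies per scenario, 10/10/10, m = 100, q = 0.05 and independent analytes. Entries are the mean share of true differences found.

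| analytes that differ | shift (SD) | chi-square | exact |
|---|---|---|---|
| 1 | 1.5 | 15% | 32% |
| 1 | 2.0 | 44% | 70% |
| 5 | 1.5 | 24% | 43% |
| 5 | 2.0 | 75% | 86% |
| 10 | 1.5 | 38% | 55% |
| 20 | 1.5 | 58% | 68% |
| 20 | 2.0 | 94.5% | 96% |
| 40 | 1.0 | 10% | 21% |
| 40 | 1.5 | 79% | 82% |
| 40 | 2.0 | 98.3% | 98.6% |
| 50 | 1.5 | 85% | 87% |

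A between-analyte correlation of 0.4 gives the same pattern. When few analytes differ and the shift is only 1 SD, the absolute loss is smaller because neither version finds much (3% v 9% with 5 analytes at correlation 0.4). With 20 per group and 5 analytes shifted by 1.5 SD, the figures are 95% v 96%.

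**Step 4: error control.** With no true difference, the chance of any discovery is about 1% with chi-square and about 5% with exact p-values. Across the scenarios the false-discovery rate with exact p-values stays at about the nominal 5% or below, within simulation error.

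**The case against.** The strongest reply is that the Protocol states nothing wrong. It names the test, the multiplicity method and the software, and does not rule out exact or Monte Carlo p-values. How a rank-test p-value is computed is often left to the analysis plan or program, and an analysis plan may exist. This stands in part. A reader might infer that the Protocol prescribes chi-square p-values; it does not. What remains is that the ordinary default, at the group size planned, does worse than a nearly free alternative.

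A reader might also infer that the cytokine analysis will miss true differences whatever the data look like. The working does not support that. The cut-off rises with the number of discoveries, and the loss fades as more cytokines differ. Ten per group is also a minimum.

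Two further extensions are tempting and fail:

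- **Choice of second-tier assays.** Section 8.1.1 lets first-tier results guide this choice, and one of its examples turns on two cytokines. It sets no significance threshold for the choice, so a conservative p-value cannot be shown to change it.
- **Section 10.2, items (2) and (3).** Both use Kruskal-Wallis tests; item (3) says "non-parametric Kruskal-Wallis tests will be done for comparison across groups (in R and SPSS". Neither states a false-discovery step. For a short list judged near 5% the approximation is adequate (ratio 1.07).

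Finally, the study is exploratory and claims no power, so no stated operating characteristic is contradicted. That is correct and is a reason to rate the point low.

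**Conclusion.** The point holds conditionally and is minor. If chi-square p-values are used at about 10 per group, those near the strictest step-up cut-off are 2.9 to 5.6 times too large. The cost is about 10 to 25 percentage points of sensitivity when few cytokines differ or effects are moderate. It is 0 to 5 points when many differ strongly. At about 20 per group it is also small for shifts of 1.5 SD or more, and may be somewhat larger for weaker shifts. The error is in the conservative direction only, so it gives no ground to distrust a positive finding.

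The sizes rest on an assumed q of 0.05, assumed shifts in one group, an assumed number of differing analytes, no ties, and the software default being used. The Protocol fixes none of these. The group size and panel size are its own.

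**What to change.** Add one sentence to section 10.1 item 2, or confirm that the analysis plan already says it: Kruskal-Wallis p-values are exact or Monte Carlo permutation p-values, with at least 100,000 resamples per analyte and ties handled by permutation, and these enter the two-stage step-up procedure.

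With 100,000 resamples, a p-value at the first cut-off has a standard error of about √(0.00048/100,000) = 0.00007, or 14% of its value. That resolves the region that matters; more resamples can be run for borderline analytes. Permuting the observed ranks also deals with ties from values below the detection limit.

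The cost is a little extra computing. When nothing differs, the chance of any false discovery rises from about 1% to the nominal 5%, which is the allowance the procedure was chosen to use. No change to section 10.2 or to the second-tier rules follows from this point.
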